2.3. Trial Design

With the small sample size and time needed to titrate up to an effective dose, this trial proposes to use a single randomized multiple-measures cross-over design (N-of-1), with results aggregated over several subjects. This design is well-suited to outcomes that are highly specific to each individual and not amenable to precise measurement across a large cohort. The heterogenous nature

of pain and irritability responses in children are more likely to be personally specific and characteristic, rather than generalizable. The behavioural pattern is reflected in the structure of the standard tools for pain assessment in SNI that rely upon a catalogue of behaviour patterns that differ from one child to the next.^{3,29,50-52}

The proposed cross-over trial will use randomization and blinding of subjects and observers with placebo controls to reduce unexpected bias. A critical distinction is that each subject will serve as their own control and experiment, allowing for a finer assessment of the treatment efficacy within each patient.

In this trial, each patient will switch between gabapentin (G) and placebo (P). The sequence of whether G precedes P (GP) or P precedes G (PG) will be randomized by the study pharmacist, and neither the clinician nor the subject (parent/caregiver) will know the sequence.

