Randomization will be undertaken by the study pharmacist, using a computer-generated randomization. Before the 2 periods (pair of active drug (G) or placebo (P)) the pharmacist will generate a random code indicating whether G or P is to be given first. The randomization table will be kept in the Research Pharmacy office, which has restricted access. In case of a serious adverse event and when necessary, the randomization of any one participant can be unmasked to the Principal Investigator. This will be done through direct contact between the pharmacist and the Principal Investigator.

Study Contacts

Contact with study participants during the trial will consist of online surveys and telephone check ins. Contacts will be scheduled to overlap with changes in dose. Each contact will last approximately 10 minutes. The following study tools will be used at study contacts (see table 4 for a schedule of assessments at the time of study contacts):

- Health Update (Appendix 6) (midway through each sequence and at study end)
- Pain Survey (Appendix) (only on the first or last day of each block, not both)
- NCCPC-R (Appendix 7)
- PROMIS-57 (Appendix 8)
- Adverse Events Log (Appendix 10)
- Concomitant Medications (Appendix 11)

When the participant begins Sequence 2, the drug will be dispensed again in person.

Follow up

Two weeks past Study End the randomization sequence for individual participants will be unblinded and shared with the participants along with their individual results. The results will be presented numerically and graphically. Graphs showing the outcomes over time on the medication and placebo arms, summarizing the dosage used at individual outcome points will be provided. This will allow participants to make decisions regarding continuing gabapentin (in consultation with their primary caregiver) and is in keeping the Strategies for Patient Oriented Research (SPOR) principles that this clinical care trial is based on. At this time, the participant's caregiver will also be given the opportunity to provide feedback to the research team via the Participation Questionnaire (Appendix 9).

For any participant that experiences a SAE, there will be an initial contact at the time of the event and appropriate evaluation undertaken by the physician investigator. Another safety follow-up visit will be scheduled within 7 days following the final study visit to review the event. Additional follow-up may be done based on the investigator's medical judgment.

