3.10. Statistical Methods

All data will be entered into a REDCap database, either directly from participants using a web-based entry system, or for those using paper, transferred from data collection sheets by a research assistant. The study cohort will be described in tables with descriptive statistics (mean, median and standard deviation) where appropriate. The primary method of analyzing the data was by systematic visual graphing of the pain scale over the exposure/placebo conditions. This is the method recommended by the CONSORT collaboration, extension for N-of-1 studies (CENT).⁵⁸

Data analysis for the primary outcome will be conducted within each N-of-1 trial and will also be aggregated across trials using measurements taken on days 11-19.

For each individual, the pain and irritability score on the NCCPC-R will be calculated over days 11-19 for both the treatment and control periods. These means will then be compared statistically using a Bayesian model, reporting the posterior mean difference using a non-informative prior for the means and variance. The posterior probability that the mean of the treatment is greater than the mean of the control will also be reported. Because of the use of non-informative priors, this analysis is very similar to a t-test.

We will also aggregate the means across participants using Bayesian linear mixed models in order to compare the average effect of the treatment as well as obtain better estimates of each individual's effect through borrowing of strength from others' data.

Additional analyses

Secondary outcomes will be assessed as follows:

- For each patient who benefits from gabapentin, the lowest dose that was effective in reducing pain scores will be calculated as the lowest dose that gives at least an 11 point reduction with no rebound over 3 days in the NCCPC-R score compared to baseline during day 11-19 on active drug. The set of lowest doses will be summarized descriptively.
- For each patient who benefits from gabapentin, the maximal effect dose will be calculated as the dose that gives the largest improvement in the NCPCC-R score compared to baseline during days 11-19 on active drug. The set of lowest doses will be summarized descriptively.

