6.2. Schedule of Enrolment, Interventions, and Assessments

Gabapentin Trial Diagrams and Summaries

Table 3 shows which assessments happen during specific phases of the trial. Table 4 shows the exact timepoint assessments are administer

Trial Design Summary

- Repeated Measures Single Cross-Over Trial (Treatment and Placebo)
- We will recruit 10 study participants. These participants will have completed the PIUO Pathway without resolution of pain. They will have severe neurological impairment and unexplained, untreated pain.
- The study participants will be randomized to treatment or placebo arms. This first session will take 25 days. During this time the treatment arm gabapentin dose will be slowly increased until an effective dose or maximum dose (60mg/kg/day) is reached, whichever comes first.
- The participants will then undergo a three-day long washout period, where neither drug nor placebo will be administered.
- Following this, the participants that were on placebo previously will switch to gabapentin treatment and those who were on gabapentin treatment will switch to placebo. This will again go on for 25 days, with the gabapentin dose increasing throughout.
- NCCPC-R, PROMIS-57 and Pain Surveys will be administered throughout the trial to obtain data
- The total participant time will be around 55 days.
- The diagram below depicts the Gabapentin trial design.

N-of-1 Design

The Gabapentin Trial will use an N-of-1 design. This means that each participant will be his or her own experiment, acting as both treatment and placebo participants. In an N-of-1 trial, each participant's treatment data is compared to his or her own placebo data, and the results are specific to

the individual participant. A small "N" such as 10 (as we are going to recruit for the Gabapentin Trial) can provide an adequate amount of data when using an N-of-1 design because 10 separate data sets and results will be produced. Multiple N-of-1 trials that are conducted on similar patients taking similar drugs can be amalgamated to give broader results.

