N-of-1 trials allow for the development of personalized medicine, which is ideal when working with a population of high heterogeneity, such as children with severe neurological impairment. Each of the participants will be unique in his or her own physical and emotional health needs. An N-of-1 trial allows the researcher to determine if treatment is effective in a specific individual, as well as the optimal dose, tolerability and potential side effects of the treatment for that individual. A standard cross-over trial may elicit the answer to the question of "Does drug X relieve pain in children with severe neurological impairment?" but an N-of-1 trial can answer the question of "Does 10mg/kg of drug X relieve pain in a 10-year-old female whose severe neurological impairment is caused by Rett Syndrome?".

The diagram below depicts a sample N-of-1 trial with five participants. Each colour represents an individual participant, and their cause of severe neurological impairment is listed on the right. Each participant will trial the treatment (in our case Gabapentin) and the placebo, in randomized order. The results (check mark = pain resolved and "X" = pain not resolved) are also coloured in to show that the results are specific to the individual. For example, the treatment that worked for the participant with Rett Syndrome may have been 30 mg/kg/day of drug X, while the effective treatment for the participant with cerebral palsy may have been 15mg/kg twice a day, because he/she was overly sensitive to the sedative effects of drug X and required a lower dose.

[figure not shown]

Table 3: Gabapentin Trial Events Schedule

Study Phase	Screening and Enrollment	Baseline Visit	Sequence 1	Study Visit	Sequence 2	Study End	Follow Up
Study Time Point	- 4 to 0 weeks	Day 1 of Period 1	Day 1 – 26 of Period 1	Day 1 of Period 2	Day 1 – 26 of Period 2	Day 26 of Period 2	1 week post Study End
Eligibility Assessment	X						
Informed Consent	X						
Demographic Information		X*					
Health Information Form		X*					
Medical History		X*					
Physical Exam		X*					
Pre-Participation Questionnaire		X					
Randomization		X					
Study Drug Dispensing		X		X			
Pain Survey			X		X	X	
NCCPC-R			X		X	X	
PROMIS-57			X		X	X	
Adverse Events Log			X		X	X	

Version 3.0 October 4, 2020 Page 38 of 45

Health Update		X		X	X	
Concomitant Medications		X		X	X	
Study Drug Accountability			X		X	
Participation Questionnaire						X

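### With one gabapentin and one placebo period per child, child-specific change between periods cannot be separated from that child's drug effect, so the per-child results are stated with too much certainty

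*Protocol*

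**What the plan says.** The design is a single cross-over. Section 3.8 (Randomization) reads "Before the 2 periods (pair of active drug (G) or placebo (P)) the pharmacist will generate a random code" for the order, so each child contributes one pair of periods and one random order. Section 6.2 gives the length ("This first session will take 25 days"), then a washout and one switch. No pair is repeated.

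Sections 2.3 and 6.2 call this an N-of-1 design and attach individual claims to it:

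- Section 2.3: each child acts as their own control, "allowing for a finer assessment of the treatment efficacy within each patient".
- Section 6.2: "An N-of-1 trial allows the researcher to determine if treatment is effective in a specific individual, as well as the optimal dose". The same paragraph contrasts this with a standard cross-over, which it says answers the group question.
- Section 3.10: each child's NCCPC-R means over days 11-19 are compared by a Bayesian model with non-informative priors, described as close to a t-test, and a posterior probability is reported. A Bayesian linear mixed model then estimates the average effect and is also meant to "obtain better estimates of each individual's effect through borrowing of strength".
- Section 3.8 (Follow up): the unblinded individual result goes to each family. "This will allow participants to make decisions regarding continuing gabapentin", in consultation with their primary caregiver.

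Section 3.6 treats the number of assessments per patient as the sample size and says that no prior data on within-patient variability were available.

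**The concern.** Within one child, gabapentin versus placebo is the same contrast as one period versus the other. An intercurrent illness, a change in other care (which section 3.3 leaves unrestricted) or ordinary fluctuation that affects one period more than the other goes into the difference read as drug effect. The two day 11-19 windows start at least 25 days apart, so such change is plausible.

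The t-like comparison takes its standard error from the scatter of days inside each period. That scatter contains no information on how far a child's level moves from one period to the next. This differs from correlation between days: it remains even if days are fully independent.

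Individual effectiveness is a stated product of the trial and reaches families, with no stated caveat that it assumes stability between periods.

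**Working it through.** **What needs no assumed SD.** Degrees of freedom for between-period variation within a child are pairs minus 1 = 1 - 1 = 0. The smallest one-sided randomisation p-value for one child is 0.5^1 = 0.50; five pairs would be needed to reach 0.5^5 = 0.031. Across 10 children it is 0.5^10 = 0.001, so the group comparison does not share this limit.

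**Inputs for the illustration.** From the protocol: 9 daily scores per period (days 11-19, daily in Table 4), hence 9 + 9 - 2 = 16 df; the 11-point change that section 3.4 calls clinically meaningful. Assumed, because the protocol gives none: no drug effect, independent days, day SD s = 8, and a child's level shifting independently in each period with SD tau = 0, 2.5, 5 or 8 points. Also chosen here: a cut-off of 0.95 on the posterior probability of benefit (gabapentin mean below placebo mean).

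**Formulas.**

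- Variance of a period mean from days alone: s²/9 = 64/9 = 7.11. Standard error used by the per-child comparison: sqrt(2 × 7.11) = 3.77, whatever tau is.
- True SD of the difference: sqrt(2(tau² + 7.11)).
- Ratio r = true SD / 3.77. The t-statistic is then r times a t variable on 16 df, so P(benefit) > 0.95 occurs with probability P(T16 > 1.746/r).
- Chance of a difference of at least 11 points favouring drug: P(Z > 11 / true SD).

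| tau | true SD | r | P(benefit) > 0.95 | difference ≥ 11 points |
|---|---|---|---|---|
| 0 | 3.77 | 1.00 | 5.0% | 0.2% |
| 2.5 | 5.17 | 1.37 | 11.0% | 1.7% |
| 5 | 8.01 | 2.13 | 21.2% | 8.5% |
| 8 | 11.93 | 3.16 | 29.4% | 17.8% |

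Simulation of 200,000 children per setting agrees within simulation error. At tau = 5, changing the day SD to 4 or 12 moves the fourth column to 33% or 15%.

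**Mixed model.** With one pair per child, the variance of the child differences is H + 2·tau² + 2s²/9, where H is the true variance of drug effects between children. Daily scores identify only the last term, so what the model can report as between-child variance of the effect is H + 2·tau². Example with H = 3² = 9, tau = 5, s = 8:

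- Total: 9 + 50 + 14.22 = 73.22.
- Apparent heterogeneity: 73.22 - 14.22 = 59, against a true 9.
- Weight kept on the child's own deviation from the group mean: 59/73.22 = 0.81. The weight that recognises period shifts: 9/73.22 = 0.12.
- Mean squared error, 10 children: raw differences 2(25 + 7.11) = 64; shrunken with estimated weight about 45 (simulated).

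Shrinkage helps, but is far too weak.

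**Group mean.** A paired t-test on 10 child differences with no drug effect and tau equal to half the day SD rejected in 5.0% of 200,000 runs at nominal 5%.

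**The case against.** Several points on the other side stand.

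- Section 3.10 sets no cut-off on the posterior probability and labels no one a responder. A reader might infer that the plan will declare false responders at the rates above; the document has no such rule. The 11-point column is nearer the protocol's yardstick, but is still a proxy: it omits the no-rebound condition, and section 3.10 applies the 11 points against baseline.
- The promise of better individual estimates is comparative, and in that sense true: shrunken estimates had lower mean squared error than raw differences in all 12 simulated settings. The design does deliver some improvement.
- Because order is randomised for each child, a child's difference is unbiased over the randomisation if there is no carry-over. What cannot be estimated is its uncertainty. A period shift common to all children is estimable across the two sequences; only child-specific shifts are not.
- Table 4 schedules NCCPC-R scores at the start of a period or at switch-over and on days 5 and 8, with Health Updates in each period. Concomitant care is recorded, and section 3.10 makes visual graphing the primary method. A shift present at the start of a period may be seen, though noisily. These measures reduce the problem without removing it.
- The section 6.2 sentence is general teaching text. The section nevertheless applies the N-of-1 label to this trial, so the claim carries over.
- Section 3.8 does not instruct families to act on the result. It says the result allows decisions, with consultation.

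None of this supplies replication within a child, and no separate analysis plan could.

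**Conclusion.** The point holds for individual results. The per-child posterior probability is valid only if nothing but treatment changes a child's level between periods, which the protocol neither states nor can check with one pair. When levels shift, the probability is too certain, and the mixed model attributes the shift to differences in drug effect. The zero degrees of freedom are a fact of the design. The size (5% rising to 29% at the 0.95 cut-off; 0.2% rising to 18% for 11 points) rests on an assumed day SD of 8, independent days and an assumed between-period SD that nothing in the document anchors.

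A reader might go further and infer that the trial's main comparison is invalid or that individual estimates are worthless. Neither follows: randomised order protects the group mean, and shrinkage lowers average error. With the average effect intact and the remedy limited to wording, this is a should-fix.

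**What to change.** In section 3.10:

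1. Make the group mean effect the only inferential claim.
2. Label each child's result 'observed difference between the two periods', and state that its posterior probability assumes no other change between periods.
3. State that the mixed model's between-child variance of the effect estimates drug heterogeneity plus twice the between-period variance. Optionally show individual estimates for an assumed range of between-period SD, for example 0, 2.5 and 5 points.

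Put the same caveat in the family report described in section 3.8, and qualify the individual-effect sentence in section 6.2.

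The cost is wording and, if chosen, one table; no visits or participants are added. The downside is that the individual claims become weaker. Repeating the gabapentin-placebo pair would supply the missing replication, but it would be a different and longer trial: two, three or four pairs give only 1, 2 or 3 df, with critical t values of 12.7, 4.3 and 3.2.
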